Withdrawal time*	Time from cecum to anus
Total procedure time*	From insertion of colonoscope to removal from the anus
Completion of split preparation	Yes = 1, no = 0
Secondary covariates	
Colon cancer	Colon cancer discovered during exam (Yes = 1, no = 0)
Sedation medications	Type, initial dose, additional doses during colonoscopy based on patient pain score and request
Secondary Outcomes	
Size of adenoma*	mm measured by open forceps
Anatomical location of adenoma	rectum, sigmoid, descending, splenic, transverse, hepatic, ascending, cecum
Located behind a fold*	Yes = 1, no = 0
Morphology of lesion*	Polypoid or flat
Pathologic diagnosis of the biopsy or snared polypectomy specimen	Adenoma (with or without advanced features), hyperplastic polyp, serrated adenoma
Immediate complications	Perforation, bleeding, hypoxia, hypotension, arrhythmia
Complications up to 30 days	Perforation, bleeding, hypoxia, hypotension, arrhythmia, severe abdominal pain requiring ER visit and/or admission to hospital

* Documented during colonoscopy and objective confirmation by digital video record of endoscope clock.

Record keeping: A digital image capturing system will be used to record the procedure to document the procedure times (insertion, arrival in the cecum, biopsy, polypectomy, end of examination), confirmation of cecal intubation (visualization of the appendix orifice and/or the ileocecal valve) and the findings during the withdrawal phase (recorded by the research assistant). The digital images will bear no personal identifier.

d. Sampling strategy

[figure not shown]
The consent covers agreement to allow the colonoscopist to randomize the method to aid colonoscope insertion and examination (chromoendoscopy with water vs. water method vs. air insufflation), and to video record and photograph the procedure for analysis.

In order to accommodate the patients and allow them time to complete the split bowel preparation in the morning of the procedure, the study procedures will be scheduled as late morning and early afternoon cases as this will give the patients more time to complete the bowel preparation.

Sample size calculation

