Examination under water may be difficult with poor preparation as the residual stool alters the color and turbidity of the water and in cases with chromoendoscopy combined with the water method, turning the water green instead of blue and impairing visibility. Our experience indicated that water exchange by intermittent suctioning of dirty water and infusion of clean water will improve the visualization of the colonic lumen. Which patient will have poor preparation, however, is unpredictable. To overcome this unavoidable problem, we have adopted this colonoscopist-controlled approach of water exchange to remove any residual stool to improve the endoscopic examination. Since quality colonoscopy is ultimately the responsibility and pride of the colonoscopist, a method that is under his/her direct control during colonoscopy is the focus of our investigation.

(f) Data collection methods, intervals, and follow-up procedures:

Follow up care after the procedure

The research coordinator will call the patients after the colonoscopy at 24 hours to conduct the post procedural evaluation including any complications and to document patient satisfaction and address any questions or concerns from the patients (routine care applicable to all research subjects). Patients are advised to contact the research team or local emergency department if they notice any post procedural discomfort or pain. Patient will be contacted by phone at 30 day to document any adverse events including post procedural complications that may lead to emergency department visits or hospitalization.

The colonoscopist will review the pathology report of all lesions biopsied or removed and will notify the patients by mail of the results and the future follow up plan. Patients are generally advised to follow up with their primary care provider unless they have a complication or a significant pathology i.e. malignant polyp that requires further management discussion and referral.

Prospective data gathering (Table 11).

Table 11: List of quality measures, their purposes, and when the data will be collected.			
Data to be monitored ^a (purpose)	Baseline	During Recover	Up to 30 days
Findings – polypoid and flat lesions (primary and secondary outcomes)	X		
Cecal intubation (secondary outcome)	X		
Total medications during colonoscopy (secondary outcome)	X		
Maximum pain score during colonoscopy (quality measure)	X	X	
Additional medications during colonoscopy (quality measure)	X		

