Demographic data interview & record review (co-variables)	X		
Medical and surgical history (co-variables)	X		
Complications - emergency department visit, hospitalization (co-variables)			X

(g) General analytic plan (statistical analysis):

Primary Hypothesis.

In patients undergoing sedated colonoscopy for screening, when all polypoid and flat lesions including diminutive ones proximal to the splenic flexure are removed by polypectomy or biopsy, the patients examined by the combined chromoendoscopy and water method will be found to have a higher proportion of individuals with at least one proximal diminutive adenoma compared with the water method alone or air insufflation method for aiding insertion of the colonoscope.

Statistical Analysis: We will summarize the variables collected by calculating the frequencies of the categorical variables [such as number of patients with at least one proximal diminutive adenoma (proximal diminutive ADR), number of adenomas detected, adenoma location, adenoma size, gender, ethnicity, etc) and calculating the mean and standard deviation of the continuous variables (such as adenoma size, volume of water used, age, BMI, etc)].

To investigate differences in ADR, we will use logistic regression models, with an outcome that is a binary variable denoting whether each subject had one or more diminutive proximal adenomas. These models will allow us to quantify the differences between the three tests and determine if the differences are statistically significant. We will account for demographic characteristics (age, gender, BMI, ethnicity, etc) and investigate how other primary covariates (procedure time, volume of water used in study, etc) affect the rate of adenoma detection. Following, we will investigate the effects of secondary covariates (colon cancer detected, sedation medications) on adenoma detection rates.

As a secondary analysis, we will investigate how the secondary outcomes vary among the three tests. We will use repeated measures ANOVA and logistic regression models to quantify the differences between tests and to determine if they are statistically significant.

Pitfalls and solution

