(b) Sources of Material: The patients' existing medical records in CPRS which contain demographic data such as age, sex, identification number, list of associated medical illnesses, medications will be reviewed. The patients' responses to the questionnaire designed for this study, the results of colonoscopy and pathology reports are specific information obtained for research purposes.

(c) Potential Risks:

Risks related to the clinical study:

Questionnaire: Inconvenience, embarrassment about revealing feelings related to the colonoscopy.

Other risks: Potential risks include confidentiality risk regarding medical and personal information. A breach of confidentiality is not anticipated due to the security procedures for research data.

Physical Risks: Water infusion in lieu of air insufflation has no known physical risks. Blood draw for checking serum electrolytes may be associated with pain and bruising at the puncture site and minimal risk of infection. Indigocarmine may be associated with nausea and itchiness but there is no reported side effect in previous studies involving the use of indigocarmine as dye staining in colonoscopy.

Psychological Risks: Water infusion in lieu of air insufflation has psychological risks of anxiety.

Social Risks: Water infusion in lieu of air insufflation has no known social risks.

Economic Risks: Water infusion in lieu of air insufflation has no known economic risks.

(2) Adequacy of Protection from Risks

(a) Recruitment and Informed Consent: For recruitment, the following will be presented to all patients attending pre-colonoscopy education class or by mail. Patients will be informed of the study and control methods of sedation and the use of water infusion in lieu of air colonoscopy with dye (study method) or without dye (study method) or conventional air colonoscopy (control method). The doctors will be conducting a study to determine if the study methods have any advantage over the control method. All patients who present to their scheduled elective colonoscopy will be invited to participate.

Participation will involve giving consent to be assigned in a random manner (according to a random list of codes generated by the computer) to one of the three ways of undergoing the examination. There will be questionnaires to be answered by all the participants.

(b) Protection against Risk:

Minimizing risks through study design:

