Risk/Benefit analysis: The risks for both groups are time spent in responding to questionnaires. The potential benefits for society are that we will gain RCT data to support or not the use of water infusion (with or without dye staining) colonoscopy performed for colorectal cancer screening.

Comprehension of the information provided: Only subjects who can read and understand the consent are enrolled. The consent form will be provided to the patient in advance of the colonoscopy (e.g. by mail, as handout at the time of pre-colonoscopy class) to enable the patient to have time to read over the descriptions, to seek other opinions and to discuss with family members or friends. The subject is asked questions and feedback is elicited to ensure that the subject is aware of the consent including risks and benefits. The questions are as follows:

Directions: Make a subjective judgment regarding item 1 below. Ask the patient question 2 through 7. The evaluator may select the appropriate language to use in formulating the questions in order to assist the subjects' understanding.

Questions:

1. Is the subject alert and able to communicate with the examiner? Yes No

2. Ask the patient to name at least two potential risks incurred as a result of participating in the study.

3. As the patient to name at least two things that will be expected of him/her in terms of patient cooperation during the study.

4. Ask the patient to explain what he/she would do if he/she decides that they no longer wish to participate in the study.

5. Ask the patient to explain what he/she would do if he/she is experiencing distress or discomfort.

6. Ask the patient if participation in this research is voluntary. True False

7. Ask the patient whether he/she could get a second opinion regarding his/her care because his/her doctor is also a researcher and these two roles can be in conflict sometimes. True False

I hereby certify that the above patient Is, Is Not, able to communicate and able to give acceptable answers to items 2, 3, 4, 5, 6 and 7 above.

Evaluator

Date

Information withheld from subjects: None

Inclusion of women and minority: Every effort appropriate to the settings will be made to include women and minority in this study.

(5) Safety and Monitoring.

This study is a MODERATE risk clinical project with the potential of uncommon serious adverse events or unanticipated problems involving risks to participants.

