The identity of the subjects will be coded so that the data sheet with patient information will be de-linked from the patient identification. The coded video recording does not contain any patient identifier. The code will be kept in separate locked location and password access-protected computer (shared drive on the VA computer). When not in use by member of the research team all hard copies of coded patient information will be locked in file cabinet in designated location with locked access (e.g. investigators' office). All patient data transferred to computerized spread sheets will be stored in computers protected by password. Password access will be available to members of the research team only. At designated time after completion of the study (e.g. after publication of results), all stored data will be destroyed or erased. These measures are taken to comply with HIPAA requirements. The site investigators will review any complications and bring the occurrence to the attention of the Institutional Review Board.

Description of how adverse events are graded:

The main interventions are conventional method versus study methods. A grading scale will be used to describe adverse events if the need arises: 1=mild, 2=moderate, 3=severe, 4=life-threatening, 5=fatal. The attribution scale is 1=definitely not related, 2=probably not related, 3=possibly related, 4=probably related, 5=definitely related to the study interventions.

Plan for adverse event reporting:

The site PI will review all adverse events.

The site PI will promptly report any serious adverse events or unanticipated problems involving risks to study subjects in accordance with regulations: reportable adverse effects arising from any research procedures will be submitted promptly to the IRB. Although they are not anticipated to occur, deaths will be reported within 24 hours to the IRB. Unanticipated problems or Serious Adverse Events in research subjects will be reported to the IRB within 5 working days of awareness of the event and written reports will be submitted to the IRB no later than 15 calendar days after the event.

All reportable adverse events will be compiled, and reported in summary form, on an annual basis to the IRB, and at the conclusion of the study.

Performance and frequency of safety reviews:

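### Nausea and itchiness, the only effects the plan attributes to indigo carmine, are not prespecified or solicited, and no by-arm comparison of them is planned

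*Combined protocol and SAP*

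**What the plan says.** **Effects attributed to the dye.** Under Human Subjects, Potential Risks (Physical Risks): "Indigocarmine may be associated with nausea and itchiness but there is no reported side effect in previous studies" of colonoscopic dye staining. No other dye-specific effect is named anywhere in the documents.

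**Complication outcomes.** Table 10 places two complication rows among the secondary outcomes. The immediate list is "Perforation, bleeding, hypoxia, hypotension, arrhythmia". The list for up to 30 days is "Perforation, bleeding, hypoxia, hypotension, arrhythmia, severe abdominal pain requiring ER visit and/or admission to hospital".

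**Data collection.** Table 11 has one complications row, "Complications - emergency department visit, hospitalization (co-variables)", marked only in the 30-day column. There is no column for the 24-hour call.

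**Open-ended contacts.** The follow-up section provides for two calls. At 24 hours: "The research coordinator will call the patients after the colonoscopy at 24 hours to conduct the post procedural evaluation including any complications". At 30 days: "Patient will be contacted by phone at 30 day to document any adverse events including post procedural complications". Under Safety and Monitoring, "The site PI will review all adverse events", with a five-level severity scale and a five-level scale for attribution to the study interventions.

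**Analysis.** The General analytic plan compares the secondary outcomes among the three methods. It specifies no by-arm table for adverse events outside that list.

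**Risk/benefit statement.** Under Human Subjects, Importance of the Knowledge: "The risks for both groups are time spent in responding to questionnaires".

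**The concern.** The combined arm is described as the water method with indigo carmine added and nothing else changed. Water plus dye against water alone is therefore a clean randomised contrast for anything the dye does, good or bad. The plan uses that contrast for detection but schedules no measurement of the two effects it names itself. The complication lists cover harms of colonoscopy and sedation, which all three arms share.

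The trial is meant to inform the addition of dye to screening of asymptomatic people, where even mild, short-lived effects belong in the trade-off. If nausea and itching are recorded only when a patient raises them, a low count in the dye arm could mean that they are rare or that nobody asked. The statement that earlier studies reported no side effect has the same weakness if those studies did not ask, and the documents do not say whether they did.

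**Working it through.** The plan gives no figure on this point, so the main check is a comparison of the text. Some arithmetic follows to show what solicited data could deliver.

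**Step 1: follow the two symptoms through the plan.**

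| Place | Nausea | Itching |
|---|---|---|
| Potential Risks | named | named |
| Table 10, immediate complications (5 items) | absent | absent |
| Table 10, complications to 30 days (same 5 plus severe abdominal pain with an ER visit or admission) | absent | absent |
| Table 11 | absent | absent |
| 24-hour call | not named; any complications | not named; any complications |
| 30-day call | not named; any adverse events | not named; any adverse events |
| Adverse-event review, grading and attribution | general | general |
| Between-arm analysis | not covered | not covered |

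The symptoms can enter the data only through the general rows, and no stated analysis then uses them.

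**Step 2: bound from zero events, if every patient is asked.** The input is 110 patients per arm (Sample size calculation). The one-sided 95% upper bound with no events is 1 − 0.05^(1/n):

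1 − 0.05^(1/110) = 0.0269, about 2.7%.

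**Step 3: detectable excess between two arms of 110.** The settings are two-sided alpha 0.05, power 0.80 and no multiplicity adjustment. The documents give no background rate, so 1% to 10% is assumed. The required number per arm, with p̄ the mean of the two rates, is

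n = [1.960·√(2p̄(1−p̄)) + 0.8416·√(p1(1−p1) + p2(1−p2))]² / (p2−p1)².

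Worked example, 2% against 12% (p̄ = 0.07):

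- 1.960·√(2 × 0.07 × 0.93) = 0.7072
- 0.8416·√(0.0196 + 0.1056) = 0.2978
- (0.7072 + 0.2978)² / 0.10² is just over 101, so 102 per arm, which is within 110.

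| Assumed background | Smallest rate (whole percent) detectable with 110 per arm | n per arm for that rate | n per arm for one point lower |
|---|---|---|---|
| 1% | 10% | 100 | 116 |
| 2% | 12% | 102 | 117 |
| 5% | 17% | 106 | 121 |
| 10% | 25% | 100 | 112 |

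The detectable excess is 9 to 15 percentage points. Solicited data would support an estimate with a confidence interval, not a powered test.

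**The case against.** The strongest reply is that the plan does have general safety capture. Study staff make two calls to patients in all arms, and the wording of the 30-day call is broad. The site PI reviews all adverse events with an attribution scale, site investigators hold weekly safety reviews, and a monitoring team meets twice a year. The investigators also limited their secondary outcomes deliberately after grant review, and they report no side effects in earlier dye studies. Leaving mild, transient symptoms to general capture is a defensible choice.

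Much of this stands, and it rules out several stronger readings that a reader might infer:

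- **That the trial cannot compare these effects by arm.** It can do so descriptively, because reports may come through the calls and every patient has a randomised arm.
- **That reporting would be uneven because staff are unblinded.** The plan says the colonoscopist and nurse cannot be blinded. The research coordinator makes the 24-hour call, and that person's blinding is not stated. The patients, who would report the symptoms, are to be blinded. Uneven reporting is possible but not shown.
- **That the safety reassurance rests on the 51 + 28 = 79 dye patients in Tables 6 and 7.** Table 7 is a preliminary look at an ongoing trial, and the statement refers to earlier colonoscopy studies in general. The figure 79 is not a ceiling.
- **That grading of adverse events is optional.** The conditional wording can simply mean that grading applies when an event occurs.

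The reply does not supply a named item, a scripted question or a planned by-arm table. A general question about complications may not bring out nausea or itching that a patient thinks trivial.

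**Conclusion.** The point holds as a minor one. The only two effects the plan attributes to the dye are not prespecified or solicited, and no by-arm comparison of them is planned. What could be compared would depend on open-ended capture of unknown completeness.

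If both symptoms were asked of everyone, zero events in 110 would exclude rates above about 2.7%. That bound is more realistic for itching than for nausea, because bowel preparation and sedation can cause nausea in any arm. Only a large between-arm excess would be detectable.

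The conclusion assumes that the study questionnaires, whose items are not reproduced, do not already ask about these symptoms. If they do, only the outcome listing and the by-arm tabulation are missing. The detectable differences rest on assumed background rates. The primary analysis is unaffected.

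Two editorial inconsistencies sit alongside. Complications are secondary outcomes in Table 10 but co-variables in Table 11. The risk/benefit sentence speaks of two groups and mentions only questionnaire time, whereas the trial has three arms, the Potential Risks section names dye effects, and Safety and Monitoring rates the study as moderate risk. Neither changes what is collected about the dye.

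**What to change.** 1. Add nausea and itching or skin reaction to Table 10 as yes/no safety items, assessed at recovery and at 24 hours.
2. Ask about both with the same scripted question in all three arms, at recovery and at the existing 24-hour call, and add that call as a column in Table 11.
3. State in the analytic plan that both will be tabulated by arm with confidence intervals as descriptive safety outcomes, with no hypothesis test. Water plus dye against water alone is the contrast that isolates the dye.
4. As editorial corrections, use one label for complications in Tables 10 and 11, and reconcile the risk/benefit sentence with the Potential Risks section and the three arms.

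The cost is two tick-boxes at existing contacts and some wording, with no extra visit or staff. The downside is that mild nausea from the preparation or sedation will be counted in every arm. That adds noise, so the results should be read as differences between arms and not as dye-arm rates alone.

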The study will utilize proximal diminutive ADR as the primary outcome. Based on prior preliminary data (Tables 5 and 7), the proximal diminutive ADR is estimated to be 14%, 34%, and 64% for air, water and combined water with chromoendoscopy, respectively. The sample size needed to detect the smallest difference (between 0.14 and 0.34) is 103 per group ($\alpha = 0.05$, power 0.80), for a total of 309. To allow for possible sample loss (e.g. due to poor bowel prep), we plan to randomize 330 subjects with 110 in each group. With these samples we can significantly determine these differences, which are equivalent to 2.5 to 3 times greater observable risk between tests.

Flow Chart Based on CONSORT Guideline:

(c) Subject recruitment.

Screening

Patient sources will include referral from primary care providers, clinical reminder on CPRS, pre-colonoscopy clinic when patients choose colonoscopy and review of colonoscopy clinic schedule to identify eligible screening patients for study. Chart review will be performed by the research coordinator for selection of patients suitable to be recruited.

Contacting patients

The research coordinator will implement the following. Initial presentation/inform patients of study will take place via telephone contact or during open access colonoscopy class. Patients interested in participating in the study will receive either mailing (those contacted by phone) or hand-out (during educational sessions) of the explanatory information and consent form to review. The phone number to call the research coordinator for questions will be provided. Those expressing interest during the educational sessions will receive a separate briefing conducted by the research coordinator after colonoscopy class regarding details of the study. Patient identifiers (name and contact phone number) will be recorded to track and document acceptance or refusal.

Day of procedure

The research coordinator will review the study with the patient and obtain informed consent. Thereafter the investigator will review the indication for colonoscopy with the patient, exclude any previously overlooked contraindication, perform the necessary physical examination, discuss and address patient questions and have the patient sign the usual clinical informed consent for the colonoscopy procedure.

(d) Description of base population and groups to be studied and method of randomization.

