Ransibrahmanakul K, [name], Mann SK, Siao-Salera R, Lim BS, Hasyagar C, Yen D, Nastaskin I, Leung FW. Comparative effectiveness of water vs. air methods in minimal sedation colonoscopy performed by supervised trainees in the US -- a RCT. *Am J Clin Med* 2010;7(3):113-118.

Leung FW, [name], Siao-Salera RM, Mann SK, Guy Jackson G. The water method significantly enhances detection of diminutive lesions (adenoma and hyperplastic polyp combined) in the proximal colon in screening colonoscopy - data derived from two RCT in US veterans. *J of Interv Gastroenterol*. In press, 2011.

[name], Ransibrahmanakul K, Toomsen L, Mann SK, Siao-Salera RM, Felix W, Leung FW. The water method combined with chromoendoscopy enhances adenoma detection. *J of Interv Gastroenterol*. In press, 2011.

Leung FW, [name], Mann SK, Friedland S, Ramirez FC. Innovation Forum - The water method significantly enhances the outcome of colonoscopy in sedated and unsedated patient. *Endoscopy*. In press, 2011.

Human Subjects

(1) Risk to Subjects

(a) Human Subjects Involvement and Characteristics: Risks common to all forms of colonoscopy (sedated or unsedated, irrespective of the clinical study) include: pain, bloating, medication reaction, bleeding, perforation, intravenous site reaction and rarely death. Sedated colonoscopy has a 1.1% risk of cardiopulmonary events (hypotension, hypoxia, arrhythmia). Death occurs in less than 0.003%.

Inclusion criteria: asymptomatic veterans scheduled for routine screening colonoscopy and agree to be randomized will be enrolled. Exclusion criteria: patients who decline to be randomized, emergent colonoscopy, evidence of colonic obstruction based on pre-colonoscopy clinical evaluation, previous history of colonic operations, hemostasis procedure, surveillance of inflammatory bowel disease, unable to give consent. Other exclusion criteria were current participation in other studies, a history of colonic surgery, a medical condition that could increase the risk associated with colonoscopy (active cardiac or pulmonary disease or other serious disease) or that would preclude a benefit from colonoscopic screening (cancer or any terminal illness), a prosthetic heart valve, anticoagulant therapy, nonmedical problems (psychiatric disorders, lack of transportation, homelessness or lack of support at home, or excessive use of alcohol), and a need for special precautions in performing colonoscopy (i.e., antibiotic prophylaxis).

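### Complications fall under a logistic regression plan that gives no finite odds ratio when an arm has no events, which is likely at the protocol's own cardiopulmonary event rate; Table 11 also mislabels them as co-variables

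*Combined protocol and SAP*

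**What the plan says.** Table 10 (Primary and secondary outcome variables) puts two complication rows under Secondary Outcomes: immediate complications, and complications up to 30 days. The second is defined as "Perforation, bleeding, hypoxia, hypotension, arrhythmia, severe abdominal pain requiring ER visit and/or admission to hospital".

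Section (g), General analytic plan, says of the secondary analysis that "we will investigate how the secondary outcomes vary among the three tests", and then: "We will use repeated measures ANOVA and logistic regression models to quantify the differences between tests and to determine if they are statistically significant". It gives no separate rule for rare events.

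Table 11, which lists the data to be monitored and their purposes, has the row "Complications - emergency department visit, hospitalization (co-variables", so it gives these events a different role from Table 10. The shorter lists of secondary outcomes in Specific Aims (b) and in the Response to reviewers (Critique 2, item 5) leave complications out.

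The only numerical rate for any of these events, apart from death, is in Human Subjects (1)(a): "Sedated colonoscopy has a 1.1% risk of cardiopulmonary events (hypotension, hypoxia, arrhythmia". On size, the sample size section states that "we plan to randomize 330 subjects with 110 in each group".

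**The concern.** A complication is a yes/no result for each patient, so of the two methods named, logistic regression is the one that fits. It works poorly when events are very few. If one arm has no events, the estimated odds ratio against an arm with events is zero or infinite, its standard error is meaningless, and the Wald p-value printed beside it tends to 1 whatever the other arm shows. The plan asks the model both to quantify differences and to judge significance. With an empty arm it cannot do the first, and its usual output cannot do the second.

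The Table 11 label adds a second problem. Emergency visits and admissions occur after randomisation, and the Response to reviewers (Critique 2, item 7) says that pain admissions may be linked to insufflated air. Events that may depend on the assigned method are outcomes, not adjustment variables, and Table 10 treats them so.

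**Working it through.** The plan gives no calculated figure for complications, so there is none to reproduce.

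**Inputs.** n = 110 per arm (sample size section). p = 0.011 (Human Subjects (1)(a)), which covers hypotension, hypoxia and arrhythmia only. All other rates are assumptions that bracket it: a composite that adds bleeding, perforation and severe pain cannot be rarer than its cardiopulmonary part, and a single component would be sparser. The rate is taken as equal across arms.

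**Step 1: empty arms.** Expected events per arm = 110 × 0.011 = 1.21. P(an arm has none) = q = (1 − 0.011)^110 = 0.2962. P(a given pair includes an empty arm) = 1 − (1 − q)² = 1 − 0.7038² = 0.50. P(at least one of three arms is empty) = 1 − 0.7038³ = 0.65.

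| Rate | Expected per arm | An arm empty | A given pair has an empty arm | At least one of three empty |
|---|---|---|---|---|
| 0.5% (assumed) | 0.55 | 0.58 | 0.82 | 0.92 |
| 1.1% (protocol, cardiopulmonary) | 1.21 | 0.30 | 0.50 | 0.65 |
| 1.5% (assumed) | 1.65 | 0.19 | 0.34 | 0.47 |
| 2% (assumed) | 2.20 | 0.11 | 0.20 | 0.29 |
| 3% (assumed) | 3.30 | 0.04 | 0.07 | 0.10 |

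With 103 patients per arm, the number before the allowance for loss, the 1.1% row becomes 0.32, 0.54 and 0.69.

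**Step 2: what the model returns.** Take 0/110 against 6/110. The log odds ratio is log(6/104) − log(0/110), which is infinite. A maximum-likelihood fit stops at about 21.7 with a standard error of about 12,491, so Wald p = 0.999. Fisher's exact test gives p = 0.029. At 0 against 12, Wald p is still 0.999, while Fisher p = 0.0004.

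**Step 3: what the alternative returns for the same data.** The risk difference is 6/110 = 5.5%. Wilson limits are 0 to 3.4% for 0/110 and 2.5% to 11.4% for 6/110. The Newcombe limits are 0.0545 − √[(0.0545 − 0.0252)² + 0.0337²] = 1.0% and 0.0545 + (0.1139 − 0.0545) = 11.4%. The exact upper 95% limit for an empty arm is 1 − 0.025^(1/110) = 3.3%.

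**Step 4: how often the choice of test changes the answer.** With one arm empty, Fisher's test reaches p < 0.05 only from six events in the other (0 against 5 gives 0.060). With a control rate of 1.1% and assumed comparator rates:

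| Comparator rate | P(control empty and comparator has 6 or more) | Power of Fisher's test |
|---|---|---|
| 2.2% | 1.0% | 1.2% |
| 3.3% | 4.6% | 5.8% |
| 5.5% | 17% | 28% |

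**The case against.** Several points on the other side are sound.

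- **Complications are not named in the analysis sentence.** They are reached through Table 10 and a general sentence on secondary outcomes, and two other lists of secondary outcomes omit them. The Response to reviewers (Critique 2, item 6) also treats additional observations as hypothesis-generating. This stands and limits the weight of the point. Table 10 is still the plan's most detailed outcome list, and no other method is offered for it.
- **The 1.1% does not describe the whole row.** This stands. For a composite it is a floor, and the range in the table above applies. The plan does not say whether a composite or single components will be analysed.
- **No Wald test is specified.** This stands. A likelihood-ratio test from the same model gives p = 0.004 for 0 against 6, although its type I error at 1.1% is about 7%. It still supplies no finite odds ratio.
- **The counts will be seen anyway.** This stands. Section (g) promises frequencies, and Human Subjects (5) has the site PI review all adverse events, with weekly safety reviews and twice-yearly monitoring meetings. None of these is a formal comparison between arms.

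A reader might infer that a real excess would be hidden. The documents do not support that: the counts would be on view, and a standard error above 12,000 is a conspicuous fitting failure. A reader might also infer from Table 11 that harms would be adjusted for and never compared between arms. Neither section (g) nor the covariate rows of Table 10 includes complications among the model covariates, so the label is an inconsistency and not a stated analysis. Nor can one say that the comparison would usually have no estimate: for a given pair the probability is about one half at 1.1%, and one empty arm leaves the contrast between the other two estimable.

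**Conclusion.** The point holds as a mismatch between method and data, plus a labelling conflict. For complications taken as secondary outcomes under Table 10, the named model has no finite odds ratio between an empty arm and an arm with events. At 1.1% and 110 per arm, at least one arm is empty with probability 0.65, ranging from 0.29 at an assumed 2% to 0.92 at an assumed 0.5%. These figures rest on equal rates across arms and on the protocol's cardiopulmonary rate standing in for outcomes it only partly covers.

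The practical loss is modest. The trial is not sized for safety: even an assumed five-fold excess (1.1% against 5.5%) gives Fisher's test only 28% power. The main gain from changing the method is therefore a usable estimate and interval, more than a better significance test. The primary outcome is unaffected. The Table 11 label needs correcting whatever the event rate.

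**What to change.** In section (g), state that complications (immediate, and up to 30 days) will be analysed as the number of randomised patients with at least one event in each arm. Give an exact 95% confidence interval per arm, and a Newcombe or exact 95% interval for each pairwise risk difference. If a test is wanted, use Fisher's exact test, which the team already uses in Tables 5 and 7. State that this replaces logistic regression and repeated measures ANOVA for these rows. In Table 11, change the purpose of the complications row from co-variables to secondary/safety outcome, so that it agrees with Table 10.

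The cost is wording only, with no new data. What is given up is covariate-adjusted odds ratios for safety, which so few events could hardly support.
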